9.2.5 Assessments in participants who prematurely stop the study

Assessments in participants who are withdrawn from the study prematurely, depend on the type and severity of the SAE. Participants who are withdrawn from the study prematurely due to the occurrence of exclusion criteria other than SAEs will not require any follow-up.

See chapter 10. for further information about follow-ups for participants who prematurely stop the study.

9.3 Procedures at each visit

9.3.1 Screening visit

At the orientation consultation/screening visit the investigator will review the case notes, investigation results (e.g., laboratory tests, gastroscopy) and interview the patient to ensure that inclusion and exclusion criteria are met. In order to comply with the inclusion criteria, pregnancy tests will be performed on all women of childbearing age. At the screening visit, the LDS and HADS questionnaires will be completed at the time of recruitment and used as screening instruments. This data will be collected using an on-line application. After inclusion, further health-related questionnaires will be completed and

the Lüscher Color Test will be performed.

A time is booked 2-4 weeks later for the second study visit. A mobile application will be downloaded onto the personal smart phone device (Symptom Tracker, Gastric Imaging & Analysis GmbH). Paper forms are available if required. During the 2-4 week "run-in" period patients will document their symptoms every day using a mobile application. A reminder will be sent to complete this electronic form every day at 21:00.

9.3.2 Study visits

On the second visit, patients will complete a combined assessment of gastric motor and sensory function off treatment with the Nottingham Test Meal, with gastric emptying documented by ¹³C-Breath Testing. On completion of the test, the test substance will be provided to the patient with instructions on how and when to take the Amara. An appointment will be made 4-6 weeks after this appointment for the third and final visit. Based on this, the start day for the intervention will also be determined.

During the 4-week intervention, 10-20 drops of Amara will be taken prior to every meal. Patients will document their symptoms every day using a mobile application. Adverse events can also be recorded. Paper forms are available if required. A reminder will be sent to complete this electronic form every day at 21:00.

Shortly before the third study visit participants receive an e-mail with a questionnaire link. All questionnaires will be completed again. If it is noted during the visit that the questionnaires has not been filled in, this can be done in the waiting room or during the visit. The patient will complete a combined assessment of gastric motor and sensory function on Amara treatment with the Nottingham Test Meal, with gastric emptying documented by ¹³C-Breath Testing. On completion of the test, in addition to the PROM, the patient will be asked about their subjective assessment of the intervention, whether ongoing treatment is desired and whether they would recommend the treatment to other patients with functional dyspepsia. Additionally, compliance with study procedures will be assessed (bottle(s) of Amara will be weighed). At the end of the study, patients are reimbursed a lump sum of 50 Swiss francs for expenses (gas, parking fee, train ticket etc.). More can be provided if an invoice supported by receipts is sent to the principal investigator.

In a subset of 20 consecutive patients, gastric electrical activity will be measured before, during and after ingestion of the Nottingham Test Meal on the second and third study visit using the non-invasive Gastric Alimetry System (high-resolution gastric mapping / electro-gastrography). Concurrent heart rate monitoring will provide an assessment of cardiovagal tone / autonomic nervous function.

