	Amara Drops will be dispensed with 10-20 drops (0.25-0.50ml) taken three times a day prior to meals for 4 weeks. Patients are free to vary the dose between these limits as considered appropriate. The amount taken will be monitored by checking the volume remaining in the bottle at the end of the 4-week intervention. During this time, patients will continue reporting the presence and severity of dyspeptic symptoms and any side effects into the app.
	At the end of the study period (Study Visit #3) the questionnaires including LCT and the ¹³ C-breath test measurement with concurrent high-resolution electro-gastrography (Gastric Alimetry System) and heart rate monitoring plus concurrent assessment of visceral sensitivity will be repeated. Additionally, the patients will be asked if their global satisfaction was better on Amara treatment, whether they wish to continue treatment and /or recommend the treatment to others with similar symptoms. Questionnaires and diary entries on side effects are also available as paper version.
Risk / Benefit Assessment	The initial assessment of patients with functional dyspepsia will adhere to international guidelines on the investigation of this condition. Amara Drops (Weleda) is a proprietary preparation that has been marketed over the counter (OTC) for many years. No serious side effects have been reported. ¹³ C-breath test gastric emptying studies and other measurements of gastric function (e.g. electro-gastrography) are indicated in patients with functional dyspepsia that do not respond to first-line, dietary management, and empirical treatment. These tests are non-invasive and not radioactive and is associated with no adverse outcomes. Clinical validation studies report that the intake of the 400ml (300kcal) Nottingham Test Meal is tolerated by all healthy controls and >95% of patients with functional dyspepsia without inducing vomiting.
Objectives:	The aim of the present study is to find out if the regular intake of Amara has effects on the perceived symptom burden reported by patients with functional dyspepsia. Since dyspeptic symptoms may be associated with abnormal gastric motor and sensory function, these aspects will be assessed by validated methods.

Outcomes:	 Primary objective / outcome measure: change in perceived symptom burden during regular intake of Amara assessed by the Leuven Dyspepsia Score between visit 1 (off treatment) and 3 (on treatment).

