3.5 Dose Rationale

Patients will take 3 x 10-20 drops of Amara before meals daily for four weeks (see section 8.1). The standard dose of this preparation is 10-15 drops before meals to "stimulate the digestive process"; however, patients are encouraged to adapt the dose to their requirements. Patient compliance will be assessed using a smart phone application that will record whether medication was taken and the severity of symptoms at the end of each day. Patient compliance (i.e. actual intake) will be checked by weighing the bottle at the end of the treatment period.

A 2-4-week run-in period between screening and the start of treatment is applied to ensure that the severity of symptoms is representative (patients tend to present during periods with relatively severe symptoms, thus run-in periods reduce the influence of spontaneous "regression to the mean" providing false positive results). The treatment period of 4-weeks is in accordance with the above-mentioned studies for other aromatic bitter substances and represents the minimum recommendation for study duration in functional gastrointestinal disorders.(15)

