4. STUDY OBJECTIVES

4.1 Overall Objective

The purpose of the present study is to evaluate whether the herbal drug Amara improves the subjective, perceived burden of abdominal symptoms in patients with functional dyspepsia. It will also assess if the treatment is well tolerated. The present study will also investigate psychological and physiological function. This additional information should provide insight into which patients benefit the most from the treatment with Amara. The results of this prospective, open-label therapeutic study will also inform the study design for any subsequent RCT study in functional dyspepsia.

4.2 **Primary Objective**

Document perceived changes in upper gastrointestinal, dyspeptic symptoms reported by patients with functional dyspepsia treated with Amara for 4 weeks, as assessed by the Leuven Dyspepsia Score between visit 1 (off treatment) and 3 (after treatment)..

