An appointment will be made 2-4-weeks later for the second study visit at which time the ¹³C gastric emptying study will be performed again. The run-in period is 2-4-weeks. This reduces the influence of spontaneous "regression to the mean" (i.e., false positive results).(15)

Gastric motor and sensory function will be assessed by ingestion of the 400ml, 300kcal Nottingham Test Meal (NTM) labelled with ¹³C acetate. This provides both an assessment of patient symptoms / visceral sensitivity to gastric filling with the 400ml liquid nutrient meal and also an assessment of gastric emptying. The 400ml NTM can be ingested by >95% of patients with functional dyspepsia.(19,

24) The ¹³C isotope is not radioactive, it takes 2-hours to complete and this technique is very appropriate for repeated assessment of gastric emptying.(16) In a subset of 20 consecutive patients, gastric electrical activity will be measured before, during and after ingestion of the Nottingham Test Meal using the non-invasive Gastric Alimetry System (high-resolution gastric mapping / electro-gastrography). Concurrent heart rate monitoring will provide an assessment of cardiovagal tone / autonomic nervous function.

The treatment period with Amara drops is four weeks per patient; participants will be instructed to take 10-20 drops of the herbal medicine Amara three times a day before meals over 28 days. This treatment period is in accordance with previous studies for aromatic bitter substances and represents the minimum recommendation for study duration in functional gastrointestinal disorders.(15) During the treatment period patients will record their symptoms using a mobile application (reminder will be sent at 21:00 every day). In addition, patients can note side effects that they perceive to be caused by Amara. If participants do not regularly provide this information, then a team member will call to ask if they have any problems.

At the end of the treatment period the participant will return to Clinic Arlesheim for repeat assessment. The LDQ and other patient related outcomes will be assessed again and ¹³C gastric emptying study will be repeated on treatment.

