11. STATISTICAL METHODS

11.1 Hypothesis

Null hypothesis: There will be no difference in the primary outcome (LDQ score) between baseline and after four weeks of Amara treatment.

Alternative hypothesis: The LDQ score after four weeks treatment is different from the LDQ-score before the treatment.

In the case of statistical significance, the null hypothesis is rejected and the described difference (reduction or increase) is found to be proven according to the alternative hypothesis.

All secondary outcomes are purely exploratory, where effects are looked at and no Null Hypothesis is tested. This study is designed to get an idea of the effect size, since an estimation of the effect size is needed in order to calculate the sample size of a subsequent confirmatory study.

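### The study schedule lets visit 3, and so the primary LDQ, fall about two weeks into treatment, against section 9.3.2 and the four-week endpoint

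*Protocol*

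**What the plan says.** Visit 3 is timed in two places.

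- **Study Schedule (table before section 1).** Visit 2 is day 1 and visit 3 is at 28±14 days. The LDQ total score is marked as the primary outcome at visits 1 and 3, and drug intake is marked at visits 2 and 3.
- **Section 9.3.2.** "An appointment will be made 4-6 weeks after this appointment for the third and final visit", counted from visit 2. The next sentence adds: "Based on this, the start day for the intervention will also be determined".

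The length of treatment is consistent elsewhere. Section 6.1 prescribes "10-20 drops of the herbal medicine Amara three times a day before meals over 28 days". Section 3.5 says that four weeks "represents the minimum recommendation for study duration in functional gastrointestinal disorders". The alternative hypothesis in 11.1 reads "The LDQ score after four weeks treatment is different from the LDQ-score before the treatment", and 11.4.2 builds the primary analysis set from patients with questionnaires at baseline and after four weeks of treatment.

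Treatment status at visit 3 has two labels. The synopsis defines the primary outcome "between visit 1 (off treatment) and 3 (on treatment"), whereas sections 4.2 and 5.1 have "between visit 1 (off treatment) and 3 (after treatment"). For the physiological tests at the same visit, 9.3.2 specifies "sensory function on Amara treatment with the Nottingham Test Meal".

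**The concern.** The two windows share an upper limit but differ by two weeks at the lower one. Staff who book from the schedule can collect the primary score at day 14 and record no deviation, although that score does not answer the stated hypothesis. The protocol itself lists four weeks as relatively brief and liable to underestimate the effect (limitations in 6.1), so an assessment at half that time runs against its own reasoning.

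The analysis sets do not settle what happens to such a patient. Under 11.4.2 the score does not come after four weeks of treatment, yet the patient followed the schedule, and the text does not say whether the score counts. The per-protocol rule (8.4, 11.4.3) need not remove the patient either, because it asks only for at least half of the medication.

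At stake is what the primary mean change represents: a four-week change, or a mixture of changes at two to four weeks. The study is meant to supply an effect size for a later trial (11.1), so a mixture would also carry forward into that planning.

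**Working it through.** **1. The two windows**

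| Source | Lower limit | Upper limit |
|---|---|---|
| Study Schedule, 28±14 days | 28 − 14 = 14 | 28 + 14 = 42 |
| Section 9.3.2, 4-6 weeks | 4 × 7 = 28 | 6 × 7 = 42 |

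The lower limits differ by 28 − 14 = 14 days; the upper limits agree. The schedule counts visit 2 as day 1 and 9.3.2 counts from the visit, which shifts the figures by at most a day and does not matter here.

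**2. Exposure at the lower limit**

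A patient who starts drug at visit 2 and is seen at day 14 has had 14/28 = 50% of the planned course. That is the most possible, since any delay in starting reduces it. In doses, the course is 28 × 3 = 84, and 14 days gives 14 × 3 = 42, again 50%. Section 8.4 calls compliance insufficient only below 50%, so a fully adherent day-14 patient can sit exactly on the per-protocol threshold and pass.

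**3. Exposure at the upper limit**

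For a visit 28 to 42 days after visit 2, setting the start 28 days before visit 3 puts it 28 − 28 = 0 to 42 − 28 = 14 days after visit 2. Exposure at visit 3 is then 28 days for every patient, with no drug-free gap. The same rule cannot rescue a day-14 visit, because the start would have to precede visit 2.

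**4. What early visits could cost (illustration only)**

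The protocol gives neither the share of patients seen early nor the time course of the effect. Assume that the effect builds linearly over 28 days, so that a day-14 patient shows half of it, and that a share s of patients is seen at day 14. Start from the protocol's standardised effect of 0.40 and 60 patients (11.2), and leave the standard deviation of the change unchanged. The mean effect is then

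d = (1 − s) × 0.40 + s × 0.20.

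Power is from a one-sample t-test on the change, two-sided alpha 0.05, n = 60.

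| Share at day 14 | d | Power |
|---|---|---|
| 0% | 0.40 | 86% |
| 10% | 0.38 | 83% |
| 25% | 0.35 | 76% |
| 50% | 0.30 | 63% |

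The first row is the value with no early visits under these inputs. It is not the protocol's stated power of 0.9, and that difference is a separate matter.

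**The case against.** The strongest reply is that one table cell is out of line and everything else is clear. Section 9.3.2 is the text that tells staff how to book, and it sets a four-week floor; the synopsis, 3.5, 6.1, 11.1 and 11.4.2 all say four weeks. If visits are booked under 9.3.2, the share at day 14 is about zero and so is the loss of power. This stands as far as size goes: nothing in the protocol says that any patient will be seen early, and the lower rows of the power table rest wholly on assumption. It does not remove the contradiction. The schedule is also an operative part of the protocol, and it makes a day-14 visit compliant.

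A reader might go further and infer, from the six-week upper limit and the words used in 4.2 and 5.1, that some patients are assessed after the drug has stopped. The protocol does not support that. The start day is set from the visit 3 appointment, the schedule marks drug intake at visit 3, and the synopsis, 6.1 and 9.3.2 place visit 3 assessments on treatment. The wording in 4.2 and 5.1 can simply mean after four weeks of treatment. A gap of 42 − 28 = 14 days would need a start on day 1, a stop at 28 days and a visit at the upper limit, contrary to the natural reading of 9.3.2.

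Nor does the bottle size point to a fault. The course needs 84 doses, and 8.1.3 gives a bottle at least 100 doses of 20 drops.

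**Conclusion.** The point holds for the lower limit. The Study Schedule permits the primary LDQ after at most about two weeks of drug. That contradicts 9.3.2, the 28-day course, and the four-week hypothesis and primary analysis, and it is half of the duration that 3.5 calls the minimum. This conclusion rests on the stated windows alone.

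The effect on the result cannot be determined from the protocol: it ranges from nothing, if all visits follow 9.3.2, to the losses illustrated above if a sizeable share is seen early and the effect builds gradually. The two labels for treatment status are a lesser inconsistency. It is worth correcting because the start-day rule carries no number and the schedule does not mention it, but it is not evidence of off-drug assessment. The design is otherwise unaffected.

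**What to change.** 1. In the Study Schedule, replace 28±14 days for visit 3 with 28 to 42 days after visit 2. Section 9.3.2 already has the right interval and should keep it.
2. State the start-day rule as a number in 9.3.2 and refer to it in the schedule: drug starts 28 days before the booked visit 3 and continues through the visit.
3. In 4.2 and 5.1, describe visit 3 as on treatment, as the synopsis does.
4. Optionally, add a sensitivity analysis of the primary outcome limited to patients with about 28 days on drug at visit 3. The daily intake record in the app and the bottle weights (8.4, 8.8) already supply the data.

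The cost is a wording amendment, slightly tighter visit booking and, if item 4 is adopted, one extra analysis run.

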10. SAFETY

10.1 Drug studies

The Sponsor's SOPs provide more detail on safety reporting.

During the entire duration of the study, all unexpected adverse events (UAW) and serious adverse events (SAEs) are collected, investigated, and documented in source documents and case report forms (CRF). Study duration encompassed the time from when the participant signs the informed consent until the last protocol-specific procedure has been completed.

10.1.1 Definition and assessment of (serious) adverse events and other safety related events

An **Adverse Event (AE)** is any untoward medical occurrence in a patient, or a clinical investigation participant administered a pharmaceutical product, and which does not necessarily have a causal relationship with the study procedure. An AE can therefore be any unfavourable and unintended sign (including an abnormal laboratory finding), symptom, or disease temporally associated with the use of a medicinal (investigational) product, whether or not related to the medicinal (investigational) product. [ICH E6 1.3]

A Serious Adverse Event (SAE) is classified as any untoward medical occurrence that:

- results in death,
- is life-threatening,
- requires in-patient hospitalization or prolongation of existing hospitalisation,

- results in persistent or significant disability/incapacity, or
- is a congenital anomaly/birth defect.

In addition, important medical events that may not be immediately life-threatening or result in death, or require hospitalisation, but may jeopardise the patient or may require intervention to prevent one of the other outcomes listed above should also usually be considered serious. [ICH E2A]

SAEs should be followed until resolution or stabilisation. Participants with ongoing SAEs at study termination (including safety visit) will be further followed up until recovery or until stabilisation of the disease after termination.

Assessment of Causality

The Sponsor-investigator makes a causality assessment of the event to the study drug, based on the criteria listed in the ICH E2A guidelines:

Relationship	Description	
Definitely	Temporal relationship	
	Improvement after dechallenge*	
	Recurrence after rechallenge	
	(or other proof of drug cause)	
Probably	Temporal relationship	
	Improvement after dechallenge	
	No other cause evident	
Possibly	Temporal relationship	
	Other cause possible	
Unlikely	Any assessable reaction that does not fulfil the above conditions	
Not related	Causal relationship can be ruled out	
*Improvement after dechallenge only taken into consideration, if applicable to reaction		

Unexpected Adverse Drug Reaction

An "unexpected" adverse drug reaction is an adverse reaction, the nature or severity of which is not consistent with the applicable product information (e.g. Investigator's Brochure for drugs that are not yet approved and Product Information for approved drugs, respectively). [ICH E2A]

Suspected Unexpected Serious Adverse Reactions (SUSARs)

The Sponsor-Investigator evaluates any SAE that has been reported regarding seriousness, causality and expectedness. If the event is related to the investigational product and is both serious and unexpected, it is classified as a SUSAR.

Assessment of Severity

Grades for severity described in the "Common Terminology Criteria for Adverse Events CTCAE Version 5.0 may be used.

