10.1.2 Reporting of serious adverse events (SAE) and other safety related events

As stated in the contract between the Clinic Arlesheim and Weleda AG, we will comply with our pharmacovigilance obligations. UAWs, SAEs and SUSARs will be reported to Weleda AG (see contact below) within a maximum of 24 hours. Any other side effects which are collected through the questionnaires will be notified to Weleda AG as soon as possible.

Address: WELEDA AG, [name]

Contact: [name], [contact], [contact]

Reporting of SAEs:

All SAEs must be reported immediately and within a maximum of $\underline{24 \text{ hours}}$ to the PI of the study. The PI will re-evaluate the SAE and make a causality assessment of the event to the study drug.

SAEs resulting in death are reported to the Ethics Committee via BASEC within 7 days.

If the possibility arises that a patient can admit the Clinic Arlesheim earlier than expected, it will lead to the discontinuation of this participant from the study. This hospital stay will not be considered as an SAE. Additionally, if a SAE is a clear result of the underlying disease, this SAE is exempted from expedited reporting.

Reporting of SUSARs

The Sponsor-Investigator needs to report SUSARs to the Ethics Committee via BASEC within 7 days, if the event is fatal, or within 15 days (all other events).

Reporting of Safety Signals

All suspected new risks and relevant new aspects of known adverse reactions that require safetyrelated measures, i.e. so called safety signals, must be reported to the Sponsor-Investigator within 24 hours. The Sponsor-Investigator must report the safety signals within 7 days to the Ethics Committee via BASEC.

Reporting and Handling of Pregnancies

Pregnant participants will be excluded from the clinical study

Periodic reporting of safety

An annual safety report is submitted once a year to the local Ethics Committee via PI.

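### The causality table in Protocol 10.1.1 is not monotone: a reaction with no other evident cause and a failed dechallenge is graded *Unlikely*, while adding a competing cause raises it to *Possibly*

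*Protocol*

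**What the plan says.** Protocol 10.1.1 gives the Sponsor-Investigator a five-grade causality table. All three upper grades require a temporal relationship.

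- *Definitely* adds improvement after dechallenge and recurrence on rechallenge, or other proof that the drug was the cause.
- *Probably* adds improvement after dechallenge and "No other cause evident".
- *Possibly* adds "Other cause possible" and has no dechallenge criterion.
- *Unlikely* is the remainder: "Any assessable reaction that does not fulfil the above conditions".
- *Not related* is a separate, lower grade: "Causal relationship can be ruled out".

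A footnote reads "Improvement after dechallenge only taken into consideration, if applicable to reaction". Its asterisk is printed on the *Definitely* row only.

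The SUSAR paragraph in the same section states: "If the event is related to the investigational product and is both serious and unexpected, it is classified as a SUSAR". It does not say which of the five grades count as related. Section 10.1.2 adds: "The PI will re-evaluate the SAE and make a causality assessment of the event to the study drug".

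**The concern.** On an ordered causality scale, evidence for another explanation should lower the drug's grade or leave it unchanged. Here *Possibly* can be reached only if another cause is possible, and *Probably* only if the reaction improved when the drug was stopped. A reaction that has neither feature has no row of its own and drops into the residual grade. A serious reaction that does not reverse quickly, in a patient with nothing else to explain it, fits that description.

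What is at stake is the step from grade to SUSAR. That step depends on the word *related*, which the protocol does not tie to the grades.

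**Working it through.** No sample size, power or alpha figure is involved. The check is to apply the table as a decision rule and list the results.

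**Inputs.** The row criteria and footnote come from the causality table in 10.1.1, the SUSAR definition from the paragraph that follows it, and the reporting routes from 10.1.2.

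**Profiles.** The temporal relationship is held present, with no rechallenge and no other proof of drug cause. What varies is dechallenge improvement (yes, no, not applicable) and other cause (no, yes), giving 3 × 2 = 6 profiles. Each is graded twice: with the footnote limited to the row that carries the asterisk, and with it extended to *Probably*.

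| Improvement after dechallenge | Other cause | Footnote on *Definitely* only | Footnote also on *Probably* |
|---|---|---|---|
| Yes | No | Probably | Probably |
| Yes | Yes | Possibly | Possibly |
| No | No | **Unlikely** | **Unlikely** |
| No | Yes | Possibly | Possibly |
| Not applicable | No | **Unlikely** | Probably |
| Not applicable | Yes | Possibly | Possibly |

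**Reading the table.**

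1. Where the reaction improved, the order is right: a competing cause moves the grade down from *Probably* to *Possibly*.
2. Where dechallenge applied and the reaction did not improve, the order is reversed under both readings: a competing cause moves the grade up from *Unlikely* to *Possibly*.
3. Where dechallenge does not apply, the order is reversed under the narrow footnote reading and correct under the wide one. So 2 of 3 dechallenge states are inverted on the narrow reading and 1 of 3 on the wide one.
4. A dechallenge that is pending or was not done is not named in the protocol. It behaves like the failed case if dechallenge counts as applicable, and like the not-applicable case otherwise.

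**From grade to report.** In 10.1.2, these routes do not depend on the causality grade:

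- To the PI: "All SAEs must be reported immediately and within a maximum of" 24 hours.
- SAEs to the manufacturer, also within 24 hours.
- SAEs resulting in death to the Ethics Committee within 7 days.

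The route that does depend on it is the SUSAR report to the Ethics Committee: 7 days if fatal, 15 days otherwise. Because deaths go to the Committee within 7 days in any case, the exposed item is the 15-day report of a non-fatal, serious, unexpected event. It is lost only if *Unlikely* is treated as unrelated.

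**The case against.** The strongest reply is that the protocol never equates *Unlikely* with unrelated. It keeps a separate *Not related* grade, and if only that grade counts as unrelated, no SUSAR is missed. This stands: the reporting consequence is conditional. The missing list is still a gap within the protocol, since the SUSAR definition turns on it. Section 10.1 says that the Sponsor's SOPs give further detail on safety reporting, so the list may exist there, but those SOPs are not part of the document.

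Second, the footnote is worded generally, and an asterisk at first use could cover the later row. That is fair for reactions to which dechallenge does not apply, and perhaps for pending ones. It does not help where dechallenge applied and failed.

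Third, grading is a matter of judgement. An assessor may take another cause to be possible whenever it has not been excluded, which gives *Possibly*. That closes the gap for that assessor, but the grade then depends on who assigns it.

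Fourth, few events are likely to be affected: 60 patients, and one serious case report in 15 years of spontaneous reporting (section 3.4). This bears on severity rather than on whether the table is right.

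A reader might infer three stronger points, which the document does not support.

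- *Tolerability will be under-counted.* Section 11.4.5 summarises side effects as percentages and does not use the causality grade.
- *Dechallenge information will usually be missing.* Section 10.1.1 has SAEs followed until they resolve or stabilise, including after study end, and section 5.4 has participants go on reporting until the effect subsides.
- *Every early SAE without another cause will be graded Unlikely.* The 24-hour limit is for reporting to the PI. No deadline forces a causality grade before dechallenge can be judged, and the pending case depends on the footnote's scope.

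**Conclusion.** The point holds as a minor defect in a rule that the protocol itself fixes. Read as written, the table is not monotone for one profile under either footnote reading: temporal relationship, no other evident cause, no improvement after an applicable dechallenge, no rechallenge or other proof. For reactions where dechallenge does not apply, is pending or was not done, the result depends on a footnote whose scope is unclear.

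The regulatory consequence is limited to the 15-day Ethics Committee report of a non-fatal, serious, unexpected event. It arises only if *Unlikely* is taken to mean unrelated. The conclusion also assumes that the rows are applied literally, with *Possibly* requiring an identifiable alternative cause. Whether the table matches the ICH guideline it cites cannot be checked from the document.

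**What to change.** In 10.1.1:

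- Reword *Possibly* as a temporal relationship where the criteria for *Probably* are not all met: another cause is possible, or improvement after dechallenge is absent, not assessable or pending.
- Restrict *Unlikely* to reactions without a plausible temporal relationship, or with another cause clearly more likely.
- Mark the dechallenge footnote on the *Probably* row as well.
- In the SUSAR paragraph, list the grades that count as related, and state that the grade is updated when dechallenge information arrives. The list matters as much as the rows: moving the affected profile to *Possibly* protects the 15-day report only if *Possibly* is on the related side.

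If the SOPs already define the related grades, the protocol should agree with them and refer to them. The cost is a wording change to one table and one paragraph, carried over to the SAE form where it uses the same grades. The downside is that a few more events are graded *Possibly* and reported.
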